4.8.7 UNSCHEDULED VISITS

An unscheduled visit is defined as an interim visit requested by the participant or investigator due to an unanticipated problem. Data recorded at these visits will be entered into the database. Only relevant and applicable unscheduled visit information will be included in the final report as deemed necessary by the lead investigator.

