4.1.2 RANDOMIZATION

A randomization schedule will be generated using a web-based program:

(www.randomization.com). An example of the format generated is given in Appendix 24. The final study randomization schedule will be generated by the CCLR Data Management Team, and provided to the research assistants for use during the study. Study investigators will remain masked to the randomization schedule until the study is completed and the database is locked.

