4.1.3 MASKING

Participants will be masked as to lens type and lens assignment (control lenses vs. test lens). Lenses dispensed to participants may be either over-labelled or have part of the label obscured, however the safety information on the outer package label of the contact lens, shall be clearly visible. Investigators will be masked as much as possible however it may not be possible to fully mask the investigators, because identifying lens markings may be visible during the biomicroscopy examination.

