7.3 PROCEDURES FOR ADVERSE EVENTS

Treatment of an adverse event will depend on its nature and severity. Based on the clinical judgment of the investigator the participant may be referred to an ophthalmologist for treatment. The investigator will attempt to determine whether the reaction is related to the test device or a result of other factors. An adverse event form (Appendix 18) will be completed for each adverse event. If both eyes are involved, a separate adverse event form will be completed *for each eye*. Whenever possible, the adverse event will be photo-documented.

Expenses incurred for medical treatment as part of study participation will be paid by the sponsor (bills and prescription receipts kept). The participant must be followed until resolution or no further change is anticipated and/or referred for further care with the appropriate health care professional and/or recorded as being under appropriate health care as per investigator's discretion. A written report will be completed indicating the subsequent treatment and resolution of the condition.

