12.6 DATA ENTRY / DATA MANAGEMENT

Data will be entered into an electronic spreadsheet. Study staff will only be able to modify the data file via password entry. The investigators will be responsible for the data integrity, and complete data entry for each visit in the CRFs and other relevant forms. The investigator will review the take home questionnaires with the participant. At the completion of the study the investigator will send the data collected to the study sponsor within approximately 5 business days after the study report is finalized.

Data analysis will not be conducted on comments which have been recorded in the source documents. Only pre-defined comments will be entered into the study database. Only relevant and applicable comments will be included in the final report as deemed necessary by the lead investigator.

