15.1.3 REPORTING AND DOCUMENTING PROTOCOL DEVIATIONS

Major protocol deviations which require changes to the research protocol or informed consent process/document or other corrective actions to protect the safety, welfare, or rights of participants or others must be reported to the ORE (as per guidelines of the ORE), using the Protocol Deviation Report Form 107 (PDRF). Information from the PDRF is provided to the Clinical Research Ethics Committee (CREC) at the next monthly meeting.

All protocol deviations (major and minor) occurring during the study will be documented and included in the final report.

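### Section 4.8.7 leaves it to the lead investigator, with no criterion and no masking requirement, which unscheduled (problem) visits appear in the final report

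*Combined protocol and SAP*

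**What the plan says.** Section 4.8.7 does three things. It defines the visit: "An unscheduled visit is defined as an interim visit requested by the participant or investigator due to an unanticipated problem". It requires full capture: "Data recorded at these visits will be entered into the database". It then restricts what is reported: "Only relevant and applicable unscheduled visit information will be included in the final report as deemed necessary by the lead investigator".

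On masking, Section 4.1.2 states: "Study investigators will remain masked to the randomization schedule until the study is completed and the database is locked". Section 4.1.3 adds that before lock "it may not be possible to fully mask the investigators, because identifying lens markings may be visible during the biomicroscopy examination".

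Adverse events follow a separate path. Section 7.3 states: "An adverse event form (Appendix 18) will be completed for each adverse event". Section 7.4 sets deadlines for notifying the sponsor (24 hours or 5 working days, depending on class) and requires reporting to the ethics office. Section 7.2 keeps transient symptoms such as dryness late in the day, itching, burning or awareness of the lens outside that path, unless the investigator considers them unexpected, severe or frequent.

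For protocol deviations, Section 15.1.3 sets a rule of complete reporting: "All protocol deviations (major and minor) occurring during the study will be documented and included in the final report".

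**The concern.** By definition, an unscheduled visit happens because something went wrong between planned visits. Here the information is collected in full and then filtered by one person, against no written standard, before it reaches the report. If that person knows, or can guess, which lens was worn, the filter can act differently on different lenses even when used in good faith.

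The hypothesis in Section 3 is that the sponsor's lens is at least as good clinically as two competitors' lenses. Comfort, dryness and visual quality are the visible primary outcomes in Section 2. A visit made because a lens was uncomfortable or vision was poor bears directly on that question. If such visits are shown for some lenses and not for others, a reader of the report cannot tell.

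**Working it through.** No figure in the plan depends on this rule, so there is nothing to reproduce. The check sets the relevant sections side by side.

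1. **Is the rule a gap or a positive instruction?** It is an instruction. Section 4.8.7 enters everything in the database and then limits the report to a selection. The terms of selection are not defined there or elsewhere in the text available.

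2. **Can the choice be made with the lens known?** Yes. Section 4.1.2 protects masking only to study completion and database lock, and a final report is normally written after lock. Section 4.1.3 accepts that lens markings may reveal the lens earlier. No section says when the choice is made, and none requires it to be masked.

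3. **Does another route guarantee that these visits reach the report?** Each candidate falls short:
   - Section 7.3 guarantees a form for each adverse event, and Section 7.4 guarantees notification of the sponsor and ethics office. Neither says that every event must be in the final report.
   - Section 7.2 means that a visit for a transient symptom may produce no adverse-event form at all.
   - Section 11.2 plans no tabulation of adverse events or unscheduled visits by lens.
   - Section 12.1 has weekly updates that state whether unscheduled visits occurred. They go to the sponsor and need not be broken down by lens.
   - Section 12.5 sends copies of the raw data to the sponsor. This makes an omission detectable by the sponsor but does not put the visit in the report.

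4. **Does the protocol require completeness elsewhere?** Yes, for deviations. Section 15.1.2 gives a missed appointment as an example of a minor deviation, and Section 15.1.3 requires every minor deviation to be reported. A visit caused by a problem with a lens carries no such requirement.

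5. **Who is affected?** Section 4.8 allows a scheduled follow-up only when the participant attends in study lenses, and it provides for rescheduling when there is no lens problem. A participant who stopped wearing a lens because of a problem does not fit that pathway. An unscheduled visit is a natural place for that information. This last step is an inference, not something the protocol states.

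6. **Scale.** Section 4.6.1 gives a maximum of 52 participants and a target of 45 completers. If each visit comes from a different participant, one omitted visit changes a lens's proportion with a problem visit by 1/52 = 1.9 percentage points, or 1/45 = 2.2 points. The documents give no expected count, so the total effect cannot be calculated.

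**The case against.** The strongest reply is that little is really hidden. Database capture is complete. Table 3 requires a symptoms and problems enquiry and an adverse-event assessment at all four visits, so problems since the last visit are asked about after each lens. Take-home ratings are completed on days 1, 3 and 6. Section 7.1 defines an adverse event broadly, and codes 17, 20 and 24 cover treatment, interruption of wear for more than a day, and other signs or symptoms that warrant classification. Visits prompted by something unanticipated may often meet the exception in Section 7.2 for unexpected symptoms. This is also a study of marketed lenses worn for one week each, which Section 6 describes as minimal risk.

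Most of this stands, and it narrows the point. It does not remove it, because none of these routes guarantees a line in the final report, and some complaints will fall below the adverse-event threshold.

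A reader might infer more than the documents support:
- *That the choice is made after unmasking.* The protocol does not time it. Relevance could be judged as each visit occurs.
- *That the whole safety comparison between lenses is compromised.* Scheduled biomicroscopy is compared by lens type under Section 11.2 and lies outside this rule. No between-lens comparison of adverse events or unscheduled visits is planned there. Part of the outcome list in Section 2 is redacted, so nothing can be said about what it holds.
- *That free-text comments should be treated the same way.* Section 12.6 gives similar discretion over comments, but there "Only pre-defined comments will be entered into the study database". Listing all comments would need new data entry and coding, which is a separate matter.
- *That a false difference of a given size would result.* Any such figure would need assumed visit counts and an assumed imbalance in omissions. The documents supply neither.

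**Conclusion.** The point holds in a limited form. Section 4.8.7 allows unscheduled visits to be selected for the final report without a criterion and without a requirement to be masked. The choice can be made with the lens known, but it cannot be said that it will be. The exposure is the presentation of unscheduled visits by lens, chiefly visits for symptoms or lens problems that do not become adverse events. It does not reach the primary ratings, the scheduled examinations or the recording and notification of adverse events.

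The size is not quantifiable from the documents beyond the change of about 2 percentage points per omitted visit shown above. The conclusion assumes that neither the adverse-event procedure in Appendix 27 nor the study contract cited in Section 19 already requires full reporting. Neither was available. If either does, Section 4.8.7 should still be brought into line with it.

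**What to change.** Replace the last sentence of Section 4.8.7 with: *All unscheduled visits will be listed in the final report by participant, period, lens worn at onset, reason, findings and outcome, and counted per lens.*

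Add that the reason for each visit and any adverse-event code are assigned before database lock, while investigators are still masked to the randomization schedule. The lens can be merged in afterwards from the schedule held by data management.

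The cost is one extra descriptive listing from data already entered, and a short coding step before lock. No visit, procedure or clinical decision changes.

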4.9 SUMMARY OF STUDY PROCEDURES

Table 3 summarizes the visits and procedures for the study.

Table 3: Summary of visits and procedures for the study.

	Visit 1 Screening / Baseline & dispensing lens pair #1	Visit 2 (+3 days of scheduled visit) 1-wk follow-up of lens pair #1 / Dispensing lens pair #2	Visit 3 (+3 days of scheduled visit) 1-wk follow-up of lens pair #2 / Dispensing lens pair #3	Visit 4 (+3 days of scheduled visit) 1-wk follow-up of lens pair #3 / and Exit
Informed consent (screening)	√			
Confirmation of inclusion/exclusion criteria	√			
Ocular & medical history	√			
Demographics	√			
VA with spectacles or refraction	√	√	√	√
Auto-refraction & keratometry	√			
Sphero-cylindrical refraction	√			
Best corrected (sphero-cyl) VA monocular and binocular	√			
HVID, palpebral aperture size	√			
Biomicroscopy	√	√	√	√
Trial fitting of study lenses	√			
Wearing time on visit day		√	√	√
Symptoms & problems enquiry	√	√	√	√
Dispense new lenses	√	√	√	
Participant ratings completed	√	√	√	√
Take-home participant	√	√	√	

	Visit 1 Screening / Baseline & dispensing lens pair #1	Visit 2 (+3 days of scheduled visit) 1-wk follow-up of lens pair #1 / Dispensing lens pair #2	Visit 3 (+3 days of scheduled visit) 1-wk follow-up of lens pair #2 / Dispensing lens pair #3	Visit 4 (+3 days of scheduled visit) 1-wk follow-up of lens pair #3 / and Exit
ratings provided				
Surface assessments	√	√	√	√
Lens fit assessments	√	√	√	√
Over Refraction (dispense)	√	√	√	
VA with contact lenses	√	√	√	√
Assessment of adverse events	√	√	√	√
Complete take home questionnaires	On days 1, 3, and 6.			
Return questionnaires		√	√	√
Exit Study				√

4.10 RECORDING FINDINGS OF INTEREST

The following variables may be recorded using a digital slit lamp system (video and still images):

- Toric stability or lens fits not considered to be clinically acceptable or associated with symptoms
- Relevant corneal and conjunctival staining
- Abnormalities of lens performance (e.g. poor fit) or appearance (e.g. manufacturing defect, non-wetting spots/surface issues)
- Additional videos (e.g. wettability, pre-lens tear film appearance, lens movement, etc.) may also be recorded in order to better understand on-eye lens performance and to help communicate this information to the sponsor.

5 MONITORING PROTOCOL ADHERENCE

Adherence to study visit windows, lens wearing schedule, and time windows around other data collection points (i.e. subjective ratings) will be monitored internally by the CCLR. Deviations from the windows described in the protocol will be reported in the weekly reports and study report.

6 POTENTIAL RISKS AND BENEFITS TO HUMAN PARTICIPANTS

This is a minimal risk study because of the use of marketed products and standard optometric assessments.

Contact lenses in this study will be worn on a daily disposable wear basis. Complications that may occur during the wearing of contact lenses include discomfort, dryness, aching or itching eyes, excessive tearing, discharge, hyperemia and variable or blurred vision. More serious risks may include photophobia, iritis, corneal edema or eye infection. Although contact lens-related infections are very infrequent, the possibility does exist. The incidence of infection due to day-wear soft lenses is 0.035%. Almost always an infection will occur only in one eye. This risk is assumed by 35-million Americans who currently wear contact lenses.

When contact lenses are worn on a daily wear basis there is a small risk of an adverse event compared to not wearing contact lenses. When contact lenses are worn on an extended wear basis, there is a significantly increased risk of an adverse reaction compared with wearing contact lenses on a daily wear basis.

Additionally, it is possible that participants may experience temporary discomfort associated with the study procedures /products/devices/eye drops (sodium fluorescein) including: burning and stinging, blurred vision, sandiness or grittiness, light sensitivity, dryness, itching, crusty eyes and foreign body sensation.

Routine clinical procedures including auto-refraction, auto-keratometry, visual acuity, anterior ocular health assessment, and contact lens fitting will be used. In addition, high magnification imaging (including video and still images) of the lens fit may be made using 35 mm or digital cameras.

There might not be direct benefits to the participants in this study. However, participation in a study may contribute to scientific research information that may be used in the development of new contact lens products. In addition, participants will receive an examination of the front part of their eyes and may have the opportunity to try a different type of soft contact lenses at no cost to them.

This study may help the study sponsor to better understand the performance of the products being used in this study.

7 ADVERSE EVENTS

7.1 ADVERSE EVENT DEFINITIONS

An 'adverse event' refers to any undesirable clinical occurrence in a participant, whether it is considered to be device-related or not. Adverse events (AE) may be classified as 'unanticipated adverse device effects,' 'serious adverse events,' 'significant adverse events,' or 'non-significant adverse events,' as defined below.

A number of conditions may result in temporary discontinuation until resolution. These include corneal infiltrates, corneal staining, limbal injection, bulbar injection or bulbar and tarsal conjunctival abnormalities.

See CCLR SOP012_v01 for a description of adverse events, including management and reporting (Appendix 27).

Classification	Definition
Serious Adverse Event	Those events that are life-threatening, or result in permanent impairment of a body function, or permanent damage to a body structure or necessitate medical (therapeutic) or surgical intervention to preclude permanent impairment of a body function or permanent damage to a body structure.
Significant Adverse Event	Those non-serious adverse events that occur with contact lens usage that are not sight-threatening but are usually symptomatic and may warrant therapeutic management and /or temporary or permanent discontinuation of contact lens wear.
Non-Significant Adverse Events	Those less severe non-serious adverse events that occur with contact lens usage that are not sight-threatening, may or may not be symptomatic and may warrant palliative management, such as ocular lubricants or temporary interruption of contact lens wear.
Unanticipated Adverse Device Effect	Adverse events in a clinical trial that were not previously identified in the protocol in terms of nature, severity, or degree of incidence. An Unanticipated Serious Adverse Device Effect is an unanticipated adverse event that is serious in nature and caused by or associated with the device and is considered reportable.

AE classification, coding (for reporting to the sponsor) and examples are provided in the following table of Contact Lens Adverse Event Classification and Reporting table:

Code	Condition	Reporting
Serious Adverse Events		
01	Presumed infectious keratitis or infectious corneal ulcer	Notify sponsor as soon as possible, within 24 hours ; ORE reporting as per requirements
02	Permanent loss of ≥ 2 lines of best spectacle corrected visual acuity (BSCVA)	
03	Corneal injury that results in permanent opacification within central cornea (6mm)	
04	Uveitis or Iritis (e.g. presence of anterior segment inflammation as described in ISO 11980, Annex B)	
05	Endophthalmitis	
06	Hyphema	

07	Hypopyon	
08	Neovascularization within the central 6mm of cornea	
00	Other serious event	
Significant Adverse Events		
11	Peripheral (outside central 6mm), non-progressive, non-infectious ulcer	Notify sponsor as soon as possible, within 5 working days ; ORE reporting as per requirements
12	Symptomatic corneal infiltrative event	
13	Superior epithelial arcuate lesions (SEALs) involving epithelial split	
14	Corneal staining \geq dense coalescent staining up to 2mm in diameter (e.g. moderate, ISO 11980 grade 3)	
15	Corneal neovascularization \geq 1.0mm vessel penetration (e.g. \geq ISO 111980 Grade 2), if 2 grade change from baseline	
16	Any temporary loss of \geq 2 lines BSCVA for \geq 2wks	
17	Any sign and/or symptom for which participant is administered therapeutic treatment or which necessitates discontinuation of lens wear for \geq 2 weeks	
10	Other significant event	
Non-significant Adverse Events		
21	Conjunctivitis (bacterial, viral or allergic)	Notify sponsor as soon as possible, within 5 working days ; ORE reporting as per requirements
22	Papillary conjunctivitis if \geq mild scattered papillae/follicles approximately 1mm in diameter (e.g. ISO 11890 Grade 2), if 2 grade change from baseline	
23	Asymptomatic corneal infiltrative events	
24	Any sign and/or symptom for which temporary lens discontinuation for $>$ 1 day is recommended (if not already classified)	
20	Other sign and/or symptom warranting classification as a non-significant adverse event	

7.2 NORMAL OR ADAPTIVE SYMPTOMS

Transient symptoms such as end-of-day dryness, lens awareness, itching or burning or other discomfort may occur with contact lens wear and may occasionally reduce wearing time. These are not reported as adverse events unless in the investigator's opinion they are unexpected in nature, severe or have a high rate of occurrence.

7.3 PROCEDURES FOR ADVERSE EVENTS

Treatment of an adverse event will depend on its nature and severity. Based on the clinical judgment of the investigator the participant may be referred to an ophthalmologist for treatment. The investigator will attempt to determine whether the reaction is related to the test device or a result of other factors. An adverse event form (Appendix 18) will be completed for each adverse event. If both eyes are involved, a separate adverse event form will be completed *for each eye*. Whenever possible, the adverse event will be photo-documented.

Expenses incurred for medical treatment as part of study participation will be paid by the sponsor (bills and prescription receipts kept). The participant must be followed until resolution or no further change is anticipated and/or referred for further care with the appropriate health care professional and/or recorded as being under appropriate health care as per investigator's discretion. A written report will be completed indicating the subsequent treatment and resolution of the condition.

7.4 REPORTING ADVERSE EVENTS

All potential Serious and Unanticipated Adverse Device Effects that are related or possibly related to participant's participation will be reported to the Principal Investigator and the sponsor within 24 hours of the investigator becoming aware of the event. The Investigator will report Serious Adverse Events to the ORE within 24 hours of the investigator becoming aware of the event and as per ORE requirements (by fax, mail/delivery, phone, or email). All fatal or life threatening events will be reported immediately to the ORE.

Significant and Non-Significant Adverse Events will be reported to the sponsor as soon as possible, but no later than 5 working days after the occurrence. The Investigator will report the event to the ORE as per ORE requirements (by fax, mail/delivery, phone, or email).

Sponsor contact details are:

[REDACTED]	[REDACTED]
	[REDACTED]

